#### 8.7.2 ADVERSE EVENTS

Adverse Events will be summarized with patient counts, percentages and event counts by MedDRA SOCs and PTs. Following categories of AEs will be summarized: TEAEs, to study drugs related TEAEs, non-serious TEAEs, serious TEAEs and related serious TEAEs, TEAEs with NCI CTCAE Grades ≥3 and related TEAEs with NCI CTCAE Grades ≥3, TEAEs leading to premature discontinuation and interruptions, TEAEs and IRR at the day of the dosing or at the

Review Status: Draft Version: 2.0 Version Date: 22-JUL-2024

next day, fatal TEAEs and related fatal TEAEs. An event will be considered study drug related if it has 'possibly', 'probably' or 'definitely' in relationship to study drug eCRF field.

Treatment-Emergent AEs, related TEAEs, serious TEAEs, related serious TEAEs, Grade 3/4/5 TEAEs, related Grade 3/4/5 TEAEs, TEAEs leading to study drug interruption or discontinuation presented by SOC and PT will also be summarized by maximum severity/CTC grade. For all TEAEs' summaries a number of patients with the event will be presented together with the total number of TEAEs.

A worst-case approach will be followed in the event of missing severity or causality data. If the severity is missing, severity grade "4" will be imputed. If causality data is missing, 'Related to study medication' will be imputed.

Listings of AE data will be created.

Summaries of all deaths reported and deaths within 28 days after the last dose of study drug along with causes of death will be created. Listing of the death data will be created.

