#### **Special Considerations related to AE Reporting**

The term "disease progression" alone should not be used when reporting AEs or SAEs, due to its lack of specificity. Rather, symptoms of disease progression should be reported. If death occurs as consequence of disease progression, this would be considered an outcome, and NOT an AE.

Example, a patient died due to a pulmonary hemorrhage secondary to tumor progression; an SAE report should be submitted with the event pulmonary hemorrhage notified as a Grade 5 (fatal).

Surgical procedures or other therapeutic interventions themselves are not AEs, but the condition for which the surgery/intervention is required is an AE and should be documented accordingly. Planned surgical measures and the condition(s) leading to these measures are not AEs if the condition(s) was (were) known before the period of observation and did not worsen during study. In the latter case, the condition should be reported as medical history.

Pregnancy is not an AE, although a patient will be withdrawn from the study if a pregnancy occurs. Refer to Section 10.3.4.1 for more information on reporting pregnancy events.

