#### 10.2. Evaluation and Classification

#### **10.2.1.** Evaluation of Severity

All AEs (including SAEs) are to be accurately recorded on the AE page of the patient's eCRF. Each event will be graded for severity using the classifications of NCI CTCAE v5.0 (NCI 2017).

For events not addressed in the NCI CTCAE v5.0 classifications, the following grading will apply:

- Mild (Grade 1) Mild; asymptomatic or mild symptoms; clinical or diagnostic observations only; intervention not indicated.
- Moderate (Grade 2) Moderate; minimal, local, or noninvasive intervention indicated; limiting age-appropriate instrumental activity of daily living.
- Severe (Grade 3) Severe or medically significant but not immediately life-threatening; hospitalization or prolongation of hospitalization indicated; disabling; limiting self-care activity of daily living.
- Life-threatening (Grade 4) Life-threatening consequences; urgent intervention indicated.
- Fatal (Grade 5) Related to AE.

During initial dosing and its respective post-observation period, any clinical finding despite its severity that represents a change from baseline (e.g., mild skin reaction, fatigue, myalgia, etc.) shall be recorded and followed until resolution.

Likewise, any clinically significant finding identified during the remaining course of the study, which represents a change from baseline would be required to be recorded by the Investigator.

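### The missing-severity rule in SAP 8.7.2 is labelled worst case but stops at Grade 4, with no visible exception for adverse events with a fatal outcome

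*SAP*

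**What the plan says.** SAP section 8.7.2 introduces the rule with "A worst-case approach will be followed in the event of missing severity or causality data" and sets the value: "If the severity is missing, severity grade '4' will be imputed". Missing causality is set to related.

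The protocol grades events by CTCAE v5.0. For events that CTCAE does not cover, section 10.2.1 gives a five-level scale whose top two levels are distinct: "Life-threatening (Grade 4) Life-threatening consequences; urgent intervention indicated" and "Fatal (Grade 5) Related to AE". The special considerations on AE reporting in section 10.1.1 give the example of a death from bleeding caused by tumor progression, for which "an SAE report should be submitted with the event pulmonary hemorrhage notified as a Grade 5 (fatal". Section 10.3.2 lists severity and outcome as separate items to be captured for every AE and SAE.

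The grade feeds several outputs in SAP 8.7.2. TEAEs, including a Grade 3/4/5 group, "will also be summarized by maximum severity/CTC grade". Fatal and related fatal TEAEs are separate categories, with no statement of how they are selected. Deaths are also reported on their own: "Summaries of all deaths reported and deaths within 28 days after the last dose of study drug along with causes of death will be created". A death listing is planned as well.

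**The concern.** A worst-case rule should assign the most severe value compatible with what is known. The causality half does so. The severity half stops one step below the top of the scale, whatever the outcome of the event. For an event with a known fatal outcome and a blank grade, Grade 4 understates the severity and sets aside information that the database already holds.

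What is at stake is the internal consistency of the safety report. The same event could stand as life-threatening in one table and as a death in another. In small cohorts a single such event would be noticed and would have to be explained.

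**Working it through.** The plan states no figure to reproduce, so the check compares the rule with the scale and then follows it through each output.

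**Inputs**
- Imputed value: Grade 4 for any missing severity (SAP 8.7.2).
- Top of the scale: Grade 5, fatal (protocol 10.2.1 and the example in 10.1.1). The list in 10.2.1 applies to events outside CTCAE, but the 10.1.1 example and the SAP's own Grade 3/4/5 group show that Grade 5 is in use generally.
- Outcome: captured separately from severity (protocol 10.3.2), so a fatal outcome can be known when the grade is missing.
- Number of fatal TEAEs with a missing grade: not given. Call it k, with k ≥ 0.

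**Effect at event level**

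Let G4 and G5 be the counts of fully graded TEAEs, with each of the k events correctly placed in Grade 5. Under the rule as written:
- Grade 5 shown = G5 − k
- Grade 4 shown = G4 + k
- Grade 4 plus Grade 5 shown = (G4 + k) + (G5 − k) = G4 + G5, so the count of Grade 3 or higher is unchanged.

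**Effect by output**

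| Output in SAP 8.7.2 | Effect of the rule |
|---|---|
| TEAE tables by maximum grade | The fatal event is shown as Grade 4. In a row where the patient already has another Grade 5 event, that patient's maximum does not change |
| Grade 3 or higher, and related Grade 3 or higher | None |
| Fatal and related fatal TEAEs, if selected by outcome | None lost, but they disagree with the tables by maximum grade |
| Fatal and related fatal TEAEs, if selected by Grade 5 | Up to k events lost |
| Death summaries and listing | None |

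With Grade 5 imputed for fatal outcomes and fatal TEAEs defined by outcome, every discrepancy in the table is zero for any k.

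**The case against.** The strongest reply is that the case should hardly ever arise. Sites are shown that a fatal event is Grade 5. SAE entry calls for complete information within 24 hours (protocol 10.3.3). The sponsor reviews SAE reports for gaps and queries them (10.3.3.1.1). The database is locked only once queries are resolved (11.1). An ungraded fatal event would have to survive all of this. It can also be argued that Grade 4 is the highest non-fatal grade and that death is an observed outcome, not something to impute. The first argument stands as to frequency. The second supports the fix, because an observed death should determine the grade.

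Three stronger readings are tempting, and the documents do not support them.

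- A reader might infer that the rule hides a death. It does not: the death summaries and the listing do not depend on the grade, and the SAP also plans separate fatal-TEAE tables. Loss from the fatal-TEAE tables would occur only if they are selected by Grade 5, which the SAP does not say.
- A reader might infer that the Phase 2a stopping rule could be missed. That trigger (protocol 4.2.4) rests on death, relationship to treatment and timing. Nothing routes it through a grade imputed at analysis.
- A reader might attach a percentage to the error. That needs a number of ungraded fatal events and a cohort denominator, and both would have to be assumed.

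One limit remains. The SAP has a heading on handling of missing data, placed just before section 8.3, with no text visible beneath it, and the table shells are in a separate document. An exception for fatal events could be there. The gap is not a fault of the plan. Section 8.7.2, however, states its own rule without qualification or cross-reference.

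**Conclusion.** The point holds as a minor correction. The visible rule is not worst case on the trial's own scale. In the rare event that it is applied to a fatal AE, it puts that event under the wrong grade in the tables by maximum grade. The resulting disagreement with the death summaries is certain if such an event exists and the rule is followed literally. Disagreement with the fatal-TEAE tables, or loss from them, depends on a selection rule that the SAP leaves open.

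The size is k events moved from Grade 5 to Grade 4. k is unknown and may well be zero. The conclusion assumes that no exception is stated in the text that cannot be seen.

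**What to change.** Replace the severity sentence in SAP 8.7.2 with:

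> If severity is missing, impute Grade 5 when the AE outcome is fatal or the AE is recorded as cause of death; otherwise impute Grade 4. Fatal TEAEs are identified by outcome, not by grade.

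If the section on handling of missing data already contains such an exception, a cross-reference from 8.7.2 is enough, together with the sentence defining fatal TEAEs.

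The cost is two sentences and one programming condition. No new data are needed, because outcome is captured for every AE and causes of death are already to be summarized. The SAP is marked as a draft, so the change can be made in the ordinary course of finalizing it.

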#### 8.7.3 LABORATORY DATA

Safety laboratory results (Serum Chemistry, Hematology, Coagulation and Thyroid Function) will be graded by NCI CTCAE v5.0. If no grading exists, values will be classified into Low/Normal/High based on laboratory normal ranges. As only the local laboratory data are collected, no quantitative summaries of the laboratory data will be created. Urinalysis results will be summarized categorically.

For laboratory results reported with a "<" sign, half of the value that follows will be used for the analysis. Results reported after ">" sign will be analyzed as is.

Shift tables classified by reference range indicator (Low, Normal, and High) and also by CTCAE toxicity grades (worst toxicity grade in a period from the first dose until final visit, not including Follow-Up period) from baseline will be presented separately by laboratory test, where applicable.

All laboratory values will be listed. A separate listing for abnormal lab values (Grade 3 and higher, and low/high values) will be presented.

#### 8.7.4 VITAL SIGNS AND OTHER SAFETY PARAMETERS

Vital signs will be summarized by descriptive statistics at each visit including change from baseline will be presented and a listing will be provided.

Local-read ECG data will be listed overall and a separate listing for any clinically significant finding in ECG values will be provided. The frequency and percentage of patients with clinically significant ECGs will be tabulated as well.

Physical Examination data will be summarized by visit. Listing of the PE data will be created.

Review Status: Draft Version: 2.0

Version Date: 22-JUL-2024

8.8	EXPLORATORY ANALYSIS			
9.	INTERIM ANALYSES			

Review Status: Draft Version: 2.0 Version Date: 22-JUL-2024

# 10. DEVIATIONS FROM ANALYSIS AS DESCRIBED IN THE PROTOCOL

The analysis of DCR by months 2, 6, 9, 12 and 15 is not appropriate and will be removed in the upcoming protocol amendment. Instead, the overall DCR is calculated and analyzed.

#### 11. PROGRAMMING SPECIFICATIONS

All outputs will be produced using SAS© version 9.4 or a later version.

The margins should be at least 1.50 inches for the binding edge and 1.0 inches for all others.

In the top left portion of each table/listing/figure, the *company name and protocol number* will be presented. On the next line, an *output number* followed by the *title* of the table/listing/figure and population information will be displayed. Horizontal lines will appear after the column heading of the table/listing. Footnotes will be put under the main body of text at the bottom of the page. The source listing number will be displayed for all tables. The *SAS program name* and its location, programmer ID, the name of the program output and its location and date of used data sets will appear bottom left and the page number will appear on the top right corner of each table/listing. The date and time of creation of table/listing will appear top right just above the page number.

Courier New 8-point bold font will be used for all tables and listings. Usually, a landscape layout is suggested for both tables and listings, but it is not mandatory. Any date information in the listing will use the date9. format; for example, 07MAY2002.

The list of tables, listings, and figures is given in section below. Shells for unique tables and listings are provided in a separate Mock-Up Tables, Figures and Listings document.
